12.2 Interim analyses

There are no interim analyses planned.

12.3 Descriptive Statistics and Exploratory Data Analysis

As hypothesized mediators, we will carefully examine behavioral (measured by DBAS, SBSRS and sleep diaries) and physiological mechanisms (measured by HRV, salivary cortisol and actigraphy). Examination of moderators will be exploratory. As potential moderators, we will examine age, baseline anxiety and depression, baseline hot flashes and baseline emotion regulation. Among these potential moderators, some will not be qualified as moderators but predict outcome regardless of the intervention assignment status (we will classify these as non-specific predictors of the outcome). For the moderator/mediator investigation, we will apply the McArthur framework. Our analysis strategy in detecting moderators and mediators is mixed effects modeling, where the McArthur approach will be embedded. We will also look at cognitive data to analyze whether interventions change cognitive domain.

12.4 Primary Analysis

Aim 1 (Primary): To evaluate the efficacy of the BBT-I in treating insomnia among breast cancer patients receiving chemotherapy.

Hypothesis 1 (Primary): BBT-I compared to an attention control group, will be associated with greater reduction of insomnia symptoms (as measured by the Insomnia Severity Inventory) from baseline to the 12 month follow up.

12.4.1 Analysis Population

Include treatment of missing data and handling of non-adherence to protocol described in 12.4.2 and 12.5.1.

12.4.2. Analysis Plan

For our primary Hypothesis 1, we will examine whether the BBT-I group will show more improvement, compared to the attention control group for insomnia symptoms measured by ISI from baseline to the 12-month follow-up. The group comparison will be made in line with the

Behavioral Intervention for Insomnia in Cancer

intention to treat principle. We will analyze the data using mixed effects (growth curve) modeling^{89,90} fully utilizing outcome data repeatedly measured four times for most participants (baseline, 6, 30, and 58 week). For estimation of mixed effect models, maximum likelihood (ML) estimation will be used. For ML estimation of these models, the Mplus program version 7.11 or above will be used.⁹¹ Data points that are missing due to subject attrition will be handled assuming that data are missing at random⁹² conditional on observed information, which is less restrictive than missing completely at random⁹² assumed in fixed effects analyses such as ANCOVA and regression analysis. In this procedure, all available cases including the ones with missing information will be included in the analyses. By including every subject who completed at least one assessment, we are not only more likely to conserve power, but also less likely to produce biased effect estimates. Given the sample and baseline covariates we will be collecting, we believe mixed effects modeling using ML is a reasonable approach. Nonetheless, we will conduct additional analyses at least for key hypotheses as a form of sensitivity analysis. For this purpose, we will apply the multiple imputation approach⁹³ utilizing various auxiliary variables in the data. We will conduct additional analyses allowing for some deviation from MAR, for example assuming MAR conditional on intervention adherence status.⁹⁴⁻⁹⁷

In our mixed effects analyses, the change in the outcome will be modeled as the key dependent variable predicted by the treatment status. The results of these longitudinal analyses can be easily converted to treatment effect at each assessment point to directly respond to our specific hypotheses. In particular, we are interested in the main effect of treatment (BBT-I vs. Control) at 12-month follow-up (58 week) assessment. The same analysis strategy will be employed for Hypothesis 2, where we will examine the treatment effects on secondary outcomes such as fatigue (measured by BFI) and cognitive difficulties (measured by Cognitive Battery). In Hypothesis 3, we will examine the mediators of treatment effects on insomnia, fatigue, and cognitive difficulties.

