Expectancy/Feedback will be obtained by 2 checklists assessing the usefulness and acceptability of the experimental interventions and intervention outcome expectancy. Participants will complete the expectancy checklist at the end of their first face-to face session and feedback questionnaire at post-intervention to assess whether they found our interventions helpful for their symptoms. For these baseline variables that are not considered as potential moderators, given our strong design based on random assignment to treatment and control groups, it is reasonable to assume that they will be balanced between the intervention and control groups (i.e., no need to worry about controlling for them). Nonetheless, we will test sensitivity of our results to presence/absence of these potential baseline covariates, especially those that differ between groups due to natural experimental error.

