12.5.1 Analysis Population

All patients contributing both baseline measurement and 12-month follow up will define the efficacy population.

Missing data

In our primary analytical strategy, we proposed to employ the statistical analysis method widely known as the mixed effects modeling approach using the maximum likelihood (ML) estimation. The use of mixed effects modeling is critical in implementing the intention-to-treat principle and therefore maintaining the validity of our inferences in the presence of missing data. Data points that are missing due to attrition and nonresponse will be handled assuming that data are missing at random (MAR¹⁰⁰), conditional on observed information. We would like to emphasize that our method is less restrictive and therefore less likely to result in bias and misleading conclusions than alternative procedures utilizing missing completely at random (MCAR¹⁰⁰), assumed in fixed effects analyses such as ANOVA and regression analysis. In analyses utilizing MCAR, cases with missing information are simply excluded from the computations. By including every participant who completes at least one assessment in the analysis utilizing MAR, we are not only more likely to conserve power, but also less likely to produce biased effect estimates. Given the sizable sample and baseline covariates assessed, we believe mixed effects modeling using ML is a reasonable approach. Nonetheless, we are aware that the assumption of missing at random conditional on observed information can be somewhat violated in practice (because we cannot possibly collect every variable related to the missing data). To address this concern, we will conduct additional analyses at least for the key hypotheses (1 & 2) as a form of sensitivity analysis. For this purpose, we will apply the multiple imputation approach¹⁰¹ utilizing various auxiliary variables in the data. Additionally, we will conduct sensitivity analysis allowing for some deviation from MAR, for example assuming MAR conditional on intervention adherence status.^{97,102-104}

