12.6.2 Sample size justification

For the primary Hypothesis 1 (BBT-I will show greater reduction of insomnia symptoms measured by ISI from baseline to the 12-month follow-up compared to the control), we estimated power in the proposed mixed effects modeling framework fully accounting for the longitudinal study design and projected attrition rate. The primary outcomes, ISI, will be measured at baseline, 6 weeks (end of treatment), 30 weeks, and 58 weeks (primary end point). For our power estimation, we used ML based mixed effects modeling assuming a linear trend. We assumed that at least 60% of variance is explained by the growth model for the primary outcome (i.e., reliability of 0.6), given that previous studies reported reliability ranging from 0.65-0.83.^{105,106} For attrition, we assumed gradually increasing attrition over time, resulting in 25% attrition by the 6-month follow-up assessment. We assumed a medium effect size, Cohen's d of 0.4 to 0.6, based on a previous study.¹⁰⁷ We also consider this range of effect size as the lower bound of a clinically meaningful treatment effect. Under this scenario, the estimated power to detect the group difference in change in ISI is 0.88-0.99 ($d=0.4$ to 0.6 , $\alpha=.05$, two-tailed) with $N=180$ (90 BBT-I, 90 control). We estimated power for the secondary Hypothesis 2 (BBT-I compared to the control will show greater improvements in fatigue and cognitive difficulties) using the same mixed effects modeling strategy. We assumed a moderate effect size of $d = 0.35$ to 0.4 , based on a previous study.^{108,109} We do not adjust for testing of multiple outcomes given that fatigue and cognitive difficulties are secondary outcomes. Under this scenario with reported reliability of 0.67 and higher,^{108,109} the estimated power to detect the group difference in change in BFI is 0.84-0.91 ($d=0.35$ to 0.4 , $\alpha=.05$, 2-tailed). For the mediator Hypothesis 3, we estimated power focusing on the main effect of the mediator on the outcome.^{98,99} We assumed a

Behavioral Intervention for Insomnia in Cancer

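### The primary ISI growth curve leaves the form of time and the baseline constraint open; the only shape named is the linear trend used for power, and no sensitivity analysis varies it

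*Combined protocol and SAP*

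**What the plan says.** Section 12.4.2 gives the model class: "We will analyze the data using mixed effects (growth curve) modeling", fitted by maximum likelihood to ISI at weeks 0, 6, 30 and 58. It then says: "In our mixed effects analyses, the change in the outcome will be modeled as the key dependent variable predicted by the treatment status". The effect at a visit is to be derived from the fitted model: "The results of these longitudinal analyses can be easily converted to treatment effect at each assessment point". Interest is in BBT-I against control at week 58. Section 12.5.2 repeats the model class without further detail.

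Neither section says whether time is linear, piecewise, curved or categorical, how it is scored, or whether baseline means are held equal. Baseline is one of the four repeated outcomes, but no constraint on it is given.

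A shape appears only in section 12.6.2: "For our power estimation, we used ML based mixed effects modeling assuming a linear trend". That section also says "we estimated power in the proposed mixed effects modeling framework", which links the power model to the analysis without fixing the analysis.

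Three sensitivity analyses are planned:
- Multiple imputation (sections 12.4.2 and 12.5.1): "we will apply the multiple imputation approach".
- Departures from missing at random: "We will conduct additional analyses allowing for some deviation from MAR".
- Baseline covariates (section 10.1): "we will test sensitivity of our results to presence/absence of these potential baseline covariates".

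None of them changes the time function.

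**The concern.** Treatment lasts 6 weeks and follow-up runs to week 58. A straight line in weeks places 52/58 = 90% of the week-58 effect after treatment has ended. With visits scored 0 to 3, it places 2/3 = 67% there. If benefit comes during treatment and then holds or fades, a straight line cannot follow it, and the error depends on how time is scored and how baseline is handled.

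The plan states no expected trajectory. Its rationale (section 2.3) points several ways: benefit that lasted in survivors, benefit lost at follow-up in a chemotherapy trial, and a preventive aim under which the arms could separate later. At stake are the size of the primary estimate, its power, and protection against choosing the form of time after seeing the data.

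**Working it through.** **Inputs from the documents.** Visits at weeks 0, 6, 30 and 58 (12.4.2). In 12.6.2: 90 per arm, two-sided alpha 0.05, d = 0.4 to 0.6, 60% of variance explained by the growth model, 25% attrition by the 6-month visit, stated power 0.88-0.99.

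**Assumptions, not in the documents.** Total SD 1; random-intercept variance 0.6, residual 0.4, no slope variance; cumulative loss 0/10/25/25% at the four visits (no week-58 figure is given). Positive values favor BBT-I.

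**Formulas.** With V = 0.6J + 0.4I, where J is all ones, and X the model's design matrix, the expected estimate is (ΣX'V⁻¹X)⁻¹ΣX'V⁻¹μ for true means μ. The SE comes from (ΣX'V⁻¹X)⁻¹. Rejection probability is Φ(δ/SE − 1.96) + Φ(−δ/SE − 1.96).

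**Step 1: the stated power.** A plain two-sample comparison at d = 0.4 has SE √(2/90) = 0.149, and 0.4/0.149 − 1.96 = 0.72 gives 0.765, so it does not reproduce 0.88. Linear models with a matching linear truth at d = 0.4 give:

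| Model | Time in weeks | Visits scored 0-3 |
|---|---|---|
| Equal baselines | 0.875 | 0.873 |
| Free baselines, slope (change) | 0.836 | 0.803 |
| Free baselines, fitted level at week 58 | 0.720 | 0.747 |

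For the first cell, SE = 0.1286 and 0.4/0.1286 − 1.96 = 1.15, so Φ = 0.875. At d = 0.6 it gives 0.997. Under these assumptions only the equal-baseline models match 0.88. Both scorings match it, so it does not show which one was used.

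**Step 2: effects that are not linear.** Linear-model estimates on change contrasts, with rejection probability in brackets for week 58:

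| Truth at weeks 6, 30, 58 | Model | Weeks: wk 58 | Weeks: wk 30 | Scores: wk 58 | Scores: wk 30 |
|---|---|---|---|---|---|
| 0.4, 0.4, 0.4 | Equal baselines | 0.33 (0.73) | 0.17 | 0.43 (0.91) | 0.28 |
| 0.4, 0.4, 0.4 | Free slope | 0.27 (0.52) | 0.14 | 0.38 (0.76) | 0.25 |
| 0.4, 0.2, 0 | Equal baselines | -0.08 (0.10) | – | +0.04 (0.06) | – |
| 0.4, 0.2, 0 | Free slope | -0.15 (0.19) | – | -0.03 (0.06) | – |
| 0.1, 0.25, 0.4 | Equal baselines | 0.39 (0.86) | – | 0.40 (0.87) | – |
| 0.1, 0.25, 0.4 | Free slope | 0.38 (0.80) | – | 0.40 (0.81) | – |

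In the fade with time in weeks, nearly all rejections favor control: only 0.5% and 0.1% favor BBT-I, against a nominal 2.5%.

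**Step 3: alternatives with equal baselines.** Categorical visits return 0.40 for the sustained effect (SE 0.1361; 0.4/0.1361 − 1.96 = 0.98; power 0.84) and 0.00 for the fade. A knot at week 6 returns 0.40 (SE 0.1306; 0.4/0.1306 − 1.96 = 1.10; power 0.87) and about 0.00. The knot model has its own limit. If the effect holds to week 30 and is gone by week 58, it reads 0.27 at week 30 (true 0.40) and +0.05 at week 58 (true 0).

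**Step 4: price if separation is truly linear in weeks, 25% missing.** Power goes from 0.875 to 0.836 with categorical visits and from 0.875 to 0.865 with the knot.

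**Step 5: slope variance.** At d = 0.4 with 25% missing, power for categorical visits and for the knot is 0.84 and 0.87 with none, 0.78 and 0.81 with slope variance 0.1 (time scaled so that week 58 = 1), and 0.68 and 0.70 with 0.3.

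**The case against.** The strongest reply is that the harm is conditional. A growth curve need not be a straight line, and linearity is stated for the power calculation only. A reader might infer that the plan commits its primary analysis to linear time; the text does not say so. The distortion also needs an early effect that holds or fades, which the plan does not predict: the rationale describes other trials and states a hope. This stands, and it limits the point to an unfixed choice whose only named candidate performs poorly in plausible cases.

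The contrast is also less open than it may look. Hypothesis 1 and section 12.4.2 speak of improvement from baseline to 12 months, change is the dependent variable, and section 12.6.2 powers a group difference in change. Together these favor a change contrast. Section 12.4.2 does mention a treatment main effect at week 58, so a level contrast remains possible. On free-baseline fitted levels, the sustained effect would read up to 0.49 at week 58 and 0.36 at week 30. The faded effect would read up to +0.13, with 13.1% of tests favoring BBT-I. Those extremes rest on the weaker reading and should not be the headline.

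A reader might also infer that the stated power is wrong, or that it says nothing about the model. Neither holds: 0.88 reproduces, and under the assumed variances it points to equal baselines while leaving the time scoring open.

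Finally, the small bias under gradual separation rests on one near-linear pattern and is not a general guarantee.

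**Conclusion.** The gap is real and worth closing. The form and scoring of time and the baseline constraint are not fixed, the only named shape is linear, and no planned sensitivity analysis tests it. If the linear power model is used for analysis, change contrasts read a sustained 0.40 SD effect as 0.27-0.43 at week 58 and 0.14-0.28 at week 30, and a faded effect as -0.15 to +0.04 at week 58. On the equal-baseline models, which reproduce 0.88 under these assumptions, the week-58 ranges narrow to 0.33-0.43 and -0.08 to +0.04.

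These are illustrations under assumed variances and attrition, not figures from the plan. Confidence is medium, because the plan may intend a flexible curve and the true trajectory is unknown.

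**What to change.** In section 12.4.2, prespecify one of two models:

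- **(a)** A likelihood-based mixed model with categorical visit, arm-by-visit terms and unstructured covariance, with baseline kept as an outcome and equal arm means at baseline. It assumes no shape over time and keeps every participant with at least one assessment, as the section requires. Using baseline ISI as a covariate instead would normally drop those with only a baseline value.
- **(b)** A growth curve with a knot at week 6 and equal baseline means. This stays within the plan's method, but the text should say that it assumes a straight line from week 6 to week 58.

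Name the test as the between-arm difference in change from baseline at the primary time point. That is week 58 in sections 12.4, 12.4.2 and 12.6.2; section 10.1 says 6 months, and the two must be reconciled. Keep any linear curve as supportive.

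In section 12.6.2, restate power for that contrast across d = 0.4 to 0.6, with explicit assumptions for week-58 attrition and slope variance.

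The cost is SAP wording and one recomputed power figure, with no new data, plus the small loss of power shown above if separation is truly linear.

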12.5 Secondary Analysis

Aim 2 (Secondary): To evaluate efficacy of the BBT-I in treating cancer-related symptoms such as cancer-related fatigue and cognitive difficulties in breast cancer patients receiving chemotherapy.

Hypothesis 2 (Secondary): BBT-I compared to an attention control group will be associated with greater improvements in fatigue and cognitive difficulties (as measured by the Brief Fatigue Inventory, and our Cognitive Battery that includes neuropsychological testing) from baseline through the 12 month follow up.

Aim 3 (Secondary): To examine potential moderators and mediators of BBT-I intervention effects on insomnia, cognitive difficulties, and fatigue. In particular, we are interested in age, depression and anxiety, emotion regulation and side effects (hot flashes) as potential moderators of the intervention effects as well as evaluating modifiable behavioral and physiological mechanisms as hypothesized mediators.

Hypothesis 3 (Secondary): In women with breast cancer receiving chemotherapy, intervention effects on insomnia, fatigue, and cognitive difficulties will be mediated by select behavioral mechanisms [i.e., maladaptive sleep behaviors (The Sleep Behavior Self-Rating Scale, sleep diaries, actigraphy), dysfunctional beliefs and attitudes (Dysfunctional Beliefs and Attitudes about Sleep) and physiological mechanisms [i.e., dysregulated circadian rhythms (measured by salivary cortisol), disrupted sleep wake cycles (actigraphy), and autonomic tone (RSA)].

As hypothesized mediators, we will carefully examine behavioral (measured by DBAS, SBSRS and sleep diaries) and physiological mechanisms (measured by HRV, salivary cortisol and actigraphy). Examination of moderators will be exploratory. As potential moderators, we will examine age, baseline anxiety and depression, baseline emotion regulation and baseline hot flashes. Among these potential moderators, some will not be qualified as moderators but predict outcome regardless of the intervention assignment status (we will classify these as non-specific predictors of the outcome). For the moderator/mediator investigation, we will apply the McArthur framework.^{98,99} Our analysis strategy in detecting moderators and mediators is mixed effects modeling, where the McArthur approach will be embedded.

